Allocation and Randomization: Treatment allocation will be done using a random, computer generated table, with an allocation ratio of 1:1, using random permuted block sizes. Stratification based on each centre (3 sites). These syringes (4*10 mls)-in sealed packages, labelled with serial numbers and no identifiers for the medication, shall be deposited in a safe drug locker, within the fridge, at the respective PACU. The actual randomization, for each patient happens as they enter into the PACU after surgery. The PACU nurse allotted for that patient will obtain the next medication package in series to be used for that patient. To ensure that the respective patient and medication is matched for subsequent analysis, the nurse will attach the medication sequence number on the patient study records, with no identifiers of actual drug. The PACU nurse shall also note down the patient hospital ID on the medication syringe, once it is taken out, to ensure there is no mix up.

Blinding: The study allocation will be blinded to patients, treating nurses, physicians, research assistant and investigators. The allocation order will be available only to the person responsible for randomizing and the pharmacists involved in the study at each centre.

Application of Intervention:

The Operating Room Protocol: Patients included in the study need to be managed according the OR protocol provided in Appendix 2. In brief, the patient will only have a GA, with local infiltration provided at the end of the surgery. Long acting opioid medications (morphine and hydromorphone) are not administered in the OR. LA infiltration is done within a range of 20-30 mls (based on laparoscopic or open surgeries) using 0.25% bupivacaine with or without adrenaline.

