PACU Stay: The actual study intervention (hence randomization) will only become applicable once the patient is moved to the PACU. Every patient will be treated as per the protocol during the intraoperative management, which primarily restricts the use of any study opioids. The details are provided in appendix 2. The nurse looking after the study patient in PACU will administer the medication as per the study protocol. This would include analgesia with equipotent doses of M or HM administered in titrated doses. Syringes will be pre-prepared from the pharmacy in EMUs; 1ml=1mg of morphine or 0.2 mg of hydromorphone. We shall consider a potency ratio of 1:5 (M: HM), considered equivalent in literature.⁽⁹⁾ Analgesia will be provided according to the following guideline. A similar method has been advised to be safe and effective for titrated analgesia in PACU.⁽²⁴⁾ Readiness to discharge from PACU and outcomes are noted at 2 hrs, or at the time of discharge to DSU.

Most Effective Opioid Analgesia in Ambulatory Surgeries: a randomized control, investigator blinded, parallel group with superiority design study of Morphine versus Hydromorphone
[name], Principal Investigator SJHH
[name], Principal Investigator HHS

PACU Protocol (titrate the opioid medication to achieve desired pain score)

- Patient to be asked for their pain score, and if it is more than 4 out of 10 (NAS): to receive the 1st dose within 5 minutes after coming to PACU: 0.04mg/kg morphine units (rounding off to the nearest 1 ml or 0.5 ml); with a maximum of 3 mg of morphine equivalents.
- Repeat doses: 0.02 mg/kg morphine units every 5-10 minutes to titrate for analgesia and side effects (rounding off to the nearest 1 ml or 0.5 ml)
- If no side effects observed-titrate to have analgesia: NAS =<4/10.
- If Nausea-Vomiting observed: record it in the CRF provided and treat it with antiemetics (Ondansetron 1-4 mg IV, Dimenhydrinate 25-50 mg)
- If patient is too sedated (<3-Ramsey Sedation Scale)-withhold the next dose and restart the bolus if the score is >3
- If respiratory depression present, withhold the next dose, treat with Naloxone if necessary.
- Ketorolac IV 15-30 mg as rescue medication if patient does not tolerate the study opioid or if the patient does not satisfy the success of satisfactory analgesia at more than 1 hr.

DSU Stay and Protocol:

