At the end of 2 hours or after satisfactory completion of primary endpoints, patients shall be transferred to DSU. At the DSU, in both groups, patients shall be given oral Oxycocet (combination of oxycodone and paracetamol) or Tylenol 3 (combination of codeine and paracetamol), as a PRN medication, if necessitated by the patient's pain. Nurses shall note down the occurrence of any pain and nausea necessitating treatment in the patient's CRF. Readiness to discharge home is noted down for each patient. The RA shall collect the CRFs from PACU and DSU and deposit safely in a locked filing cabinet.

Planned Outcomes: Our combined primary outcome will be proportion of patients with SAME, as compared between the 2 groups. Analgesia will be based on NAS 0-10 (appendix 3), and PONV will be based on VDS 0-5 (appendix 3). These observations will be made at the end of 2 hrs or before (corresponding to the time of discharge from PACU), by the PACU nurse, in the specified CRF. All the other outcomes to be recorded within the hospital, along with the time of their measurement and proposed analysis method are noted in table 1.

Sample Size Calculation: It was calculated based on the primary, binary outcome of proportion of patients with SAME, which will be compared using a chi-square test. According to literature,

Most Effective Opioid Analgesia in Ambulatory Surgeries: a randomized control, investigator blinded, parallel group with superiority design study of Morphine versus Hydromorphone
 [name], Principal Investigator SJHH
 [name], Principal Investigator HHS

approximately 30%-40% of patients are provided with inadequate analgesia after their AS,^(25, 26) with a similar number also known to suffer from PONV after AS.^(3, 24) Our chart reviews suggests that approximately 20% of patients suffer from inadequate analgesia with PONV using morphine. For a 2-sided test, with an alpha of 0.05 and a power of 90%, and with an estimated effect size of 10% (p1= 80% and p2= 90%), a sample size of 266 per group was calculated. However, for recruitment we shall have a target of 275 per group, for a total of 550 patients (rounding off). For the primary outcome analysis, we expect minimal loss through attrition as the study involves a follow up of few hours. The expected recruitment is approximately 20 cases per month at each of the 3 sites. We expect the trial to run for 10-12 months.

Table 1: Study Outcomes, and their Measurement and Analysis

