Risk Assessment and Protocol Adherence: This trial does not entail any higher risk than the standard of care to the patients. This is a pragmatic trial and involves the use of medications of known benefit and in clinically acceptable doses. It also involves using only short acting opioids in the form of fentanyl or sufentanil or remifentanil in small boluses or infusion. Although for some this might differ from their normal practice, we do not anticipate this to be a major issue as the surgeries would be of 1-2 hrs duration and can be effectively and safely managed with short acting opioids until patients are shifted to PACU. Protocol also involves the use of study medications in PACU at an initial dose of 0.05mg/kg, followed by 0.03/mg/kg EMU boluses. Studies have shown that IV Morphine titration in PACU, after moderately painful surgeries

Most Effective Opioid Analgesia in Ambulatory Surgeries: a randomized control, investigator blinded, parallel group with superiority design study of Morphine versus Hydromorphone

[name], Principal Investigator SJHH

[name], Principal Investigator HHS

require a mean morphine dose of $0.17 +/ - 0.10$ mg/kg.^(17,28) Only doses as high as 0.15mg/kg were found to be associated with significant adverse effects.⁽²⁹⁾

Potential Pitfalls (Study Limitations): Despite being a randomized study, there exists the possibility of bias due to unequal distribution of unknown covariates. The primary outcome of SAME is being measured using subjective pain scale of NAS and VDS for emesis. Although there are inherent limitations of such scales, we think they are widely used in practice and are well validated. We have considered a potency ratio of 1: 5 (M: HM) as it is commonly used and supported by the literature. However, we do accept that there is a much wider range described in some studies.

STUDY SIGNIFICANCE:

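### The protocol states two different dosing rules for the study opioid in PACU, so the Risk Assessment does not describe the regimen set out in the PACU Protocol

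*Combined protocol and SAP*

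**What the plan says.** The dosing rule for the study drug appears twice in the combined protocol and SAP (Version 5).

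- **PACU Protocol** (under Application of Intervention, PACU Stay). A patient whose pain score is above 4 is "to receive the 1st dose within 5 minutes after coming to PACU: 0.04mg/kg morphine units", "with a maximum of 3 mg of morphine equivalents". Then: "Repeat doses: 0.02 mg/kg morphine units every 5-10 minutes to titrate for analgesia and side effects". Doses are rounded to the nearest 1 ml or 0.5 ml.
- **Risk Assessment and Protocol Adherence.** "Protocol also involves the use of study medications in PACU at an initial dose of 0.05mg/kg, followed by 0.03/mg/kg EMU boluses". No maximum, interval or rounding is given. The section then cites a mean titration requirement of 0.17 ± 0.10 mg/kg from other studies and adds: "Only doses as high as 0.15mg/kg were found to be associated with significant adverse effects".

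The syringes are made up so that "1ml=1mg of morphine or 0.2 mg of hydromorphone". One rule in morphine equivalents therefore serves both arms.

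**The concern.** The two sections describe the same drug at the same step with different numbers. The document has no precedence statement, and the Risk Assessment is not an amendment log, so its figures cannot be set aside as superseded text.

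Three things are at stake.

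- **Consistency of the intervention.** Three sites will work from this document. Dosing instructions drawn from different sections would give different regimens. Appendix 1 also provides for the OR anesthesiologist to start the protocol when the PACU is on hold, yet Appendix 2, written for that anesthesiologist, contains no study-opioid doses.
- **Judging adherence.** Data Management and Quality Control requires protocol violations to be noted. A first dose of 0.05 mg/kg agrees with one section and breaches the other.
- **The risk justification.** The section that argues the doses are acceptable does not describe the regimen in the PACU Protocol.

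Dose per step also bears on listed outcomes: total analgesic dose, sedation, respiratory depression, and the PONV part of the primary outcome.

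**Working it through.** The plan derives no dosing figure that could be reproduced. Its sample size of 266 per group uses no dosing input and is unaffected.

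**Inputs.** PACU Protocol: 0.04 mg/kg first dose, 3 mg maximum, 0.02 mg/kg repeats. Risk Assessment: 0.05 mg/kg first dose, 0.03 mg/kg repeats, no maximum stated. Body weights are assumed for illustration.

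**1. Could units, rounding or a misprint explain the gap?**

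- Units: no. Both sections use morphine equivalents.
- Rounding: no, because the mg/kg rules themselves differ. At 60 kg with 0.5 ml rounding, first doses are 2.4 → 2.5 ml against 3.0 ml, and repeats are 1.2 → 1.0 ml against 1.8 → 2.0 ml. Rounding can hide the gap at some weights: at 75 kg with 1 ml rounding (half up), repeats of 1.5 and 2.25 ml both become 2 ml.
- Misprint: the extra slash in the Risk Assessment's repeat dose looks like a typing slip, but 0.05 and 0.03 are legible.

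**2. Ratios (no assumption needed).** First dose: 0.05 / 0.04 = 1.25. Repeat: 0.03 / 0.02 = 1.50.

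**3. Doses in mg of morphine equivalents, before rounding (dose = mg/kg × weight).**

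| Weight | First dose, PACU Protocol | First dose, Risk Assessment as written | Repeat, PACU Protocol | Repeat, Risk Assessment |
|---|---|---|---|---|
| 50 kg | 2.0 | 2.5 | 1.0 | 1.5 |
| 75 kg | 3.0 | 3.75 | 1.5 | 2.25 |
| 100 kg | 3.0 (4.0 before the maximum) | 5.0 | 2.0 | 3.0 |

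At 100 kg the first-dose ratio is 5.0 / 3.0 = 1.67.

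**4. Where a 3 mg maximum would bind.** PACU Protocol: 3 / 0.04 = 75 kg. If the same maximum were applied to the Risk Assessment dose: 3 / 0.05 = 60 kg.

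**5. First dose plus six repeats at 75 kg.**

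- PACU Protocol: 3.0 + 6 × 1.5 = 12.0 mg.
- Risk Assessment, no maximum: 3.75 + 6 × 2.25 = 17.25 mg.
- Risk Assessment with the 3 mg maximum applied: 3.0 + 6 × 2.25 = 16.5 mg.

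**6. Against the document's own reference figures.** The text does not say whether 0.15 mg/kg is a single or a cumulative dose. Read as cumulative, with no maximum binding, the number of repeats needed to reach or pass a level is the next whole number at or above (level − first dose) / repeat dose.

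- 0.15 mg/kg, PACU Protocol: (0.15 − 0.04) / 0.02 = 5.5, so 6 repeats.
- 0.15 mg/kg, Risk Assessment: (0.15 − 0.05) / 0.03 = 3.33, so 4 repeats.
- 0.17 mg/kg, PACU Protocol: (0.17 − 0.04) / 0.02 = 6.5, so 7 repeats.
- 0.17 mg/kg, Risk Assessment: (0.17 − 0.05) / 0.03 = 4.0, so 4 repeats.

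Read as a single dose, 0.15 mg/kg is 0.15 / 0.04 = 3.75 times one first dose and 0.15 / 0.05 = 3 times the other. On either reading the comparison depends on which regimen is meant.

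**The case against.** The strongest reply is that the two passages have different roles. The PACU Protocol is laid out as instructions, with a trigger, interval, rounding, maximum and withholding rules. The Risk Assessment has one descriptive sentence that could not be followed as an order on its own. Staff would probably use the former. That is plausible, but it is an inference: no text says so, and the Risk Assessment states its figures as what the protocol involves.

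Several narrower points stand and limit the claim.

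- The Risk Assessment is silent on a maximum; it does not reject one. The direct conflict is in the two mg/kg pairs. Whether the maximum applies is an open question, and the 60 kg and 16.5 mg figures illustrate one answer to it.
- The six-repeat totals hold the number of repeats equal. Dosing is titrated to pain and withheld for sedation or respiratory depression, so larger steps may need fewer repeats and the difference in total dose may be smaller.
- The Risk Assessment names the larger doses. If the PACU Protocol regimen is the one given, the risk text discusses a heavier regimen than patients receive. It is still not a discussion of that regimen.
- Allocation is blinded, stratified by centre and made "with an allocation ratio of 1:1". A site difference would fall on both arms and would not by itself bias the treatment comparison.
- Divergent dosing between sites is a risk. The documents do not show that it has happened.

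**Conclusion.** The contradiction is real and must be fixed. The Risk Assessment first dose is 25% above the PACU Protocol figure and its repeat dose is 50% above; these ratios rest on no assumption. The milligram figures rest on the assumed weights and ignore rounding. The 12.0, 16.5 and 17.25 mg totals also assume 75 kg and six repeats under each rule. The repeat counts of 6 and 4 assume that 0.15 mg/kg is cumulative and that no maximum binds.

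The sample size and the validity of the randomized comparison are not in question. The finding rests on a single point: an intravenous opioid intervention needs one stated regimen and a risk justification that refers to it. Confidence is high, because the conflict is visible in the text itself.

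**What to change.** The sponsor should reconcile the two sections so that the same first dose, the same repeat dose and the same statement on the maximum appear in both. The comparison with the 0.17 and 0.15 mg/kg figures should then be rechecked for that regimen, saying whether 0.15 mg/kg is a single or a cumulative dose. Any dosing instructions already issued to the three sites should be checked against the reconciled text, including those for the OR anesthesiologist who may start the protocol. Which regimen is right is for the sponsor and the clinical investigators to decide; this review proposes none.

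The cost is a wording correction in one of the two sections and a check of site materials. The sample size and analysis need no change.

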APPENDIX 1: Study Patient Case Record Form with Details to be Recorded

DEMOGRAPHICS AND PATIENT INFORMATION TO BE OBTAINED FROM PATIENT RECORDS

Study Number: Site: SJH MUMC JH

1	Patient's Hospital ID Number		
2	Age		
3	Gender	M	F
4	Height		
5	Weight		
6	Allergy to NSAIDS	Y	N
7	Allergy to LAs	Y	N

INFORMATION TO BE GAINED FROM THE PATIENT MEETING

1	APFEL Score (for PONV prediction)		Collected on 4 items- separately
2	HADS Score (Hospital Anxiety Depression Scale)		Collected on 14 items- separately
3	PCS (Pain Catastrophizing Scale)		Collected on 13 items - separately
4	Presence of Preoperative Pain in the Surgical Area	Y	N
5	If YES: is it Mild/ Moderate/ Severe		
6	Presence of Chronic Pain (>4 months) in Other Parts of the Body	Y	N

Most Effective Opioid Analgesia in Ambulatory Surgeries: a randomized control, investigator blinded, parallel group with superiority design study of Morphine versus Hydromorphone
 [name], Principal Investigator SJHH
 [name], Principal Investigator HHS

7	If YES: is it Mild/ Moderate/ Severe		
---	--------------------------------------	--	--

SURGICAL DETAILS TO BE OBTAINED FROM THE SURGICAL RECORDS

1	Date of Surgery		
2	Diagnosis (Intraoperative)		
3	Actual Surgical Procedure		
4	Laparoscopic or Open	L O	
5	Surgeon		Initials
6	Start Time of Surgery		
7	End Time of Surgery		
8	Duration of Surgery		
9	Total Local Anesthetic Infiltration (mls)		

ANESTHESIA DETAILS TO BE OBTAINED FROM THE ANESTHETIC RECORD

1	Anesthesiologist		Initials
2	Dexamethasone 4mg or 8mg	Y N	
3	Midazolam	1 mg 2 mg	
4	Propofol (total dose used)		
5	Remifentanyl (total dose used)		
6	Fentanyl (total dose used)		
7	Sufentanil (total dose used)		

Most Effective Opioid Analgesia in Ambulatory Surgeries: a randomized control, investigator blinded, parallel group with superiority design study of Morphine versus Hydromorphone
 [name], Principal Investigator SJHH
 [name], Principal Investigator HHS

8	Any continuous infusion used	Propofol  Remifentanyl 	
9	Ondansetron Prophylaxis Dose		Given prior to extubation
10	Was there a delay in transferring patient to the PACU (applicable when the PACU is on hold-and protocol needs to be initiated by the OR anesthesiologist)	Y N	

APFEL SCORE: for Prediction of Post-Operative Nausea Vomiting

RISK FACTOR	SCORE (each gets 0 or 1)
Postoperative Opioids	
Non-smoker	
Female Gender	
History of PONV or Motion Sickness	
Total Score	

Most Effective Opioid Analgesia in Ambulatory Surgeries: a randomized control, investigator blinded, parallel group with superiority design study of Morphine versus Hydromorphone
[name], Principal Investigator SJHH
[name], Principal Investigator HHS

PCS: Patient Catastrophizing Score: Copyright 1995 Michael JL Sullivan

Everyone experiences painful situations at some point in their lives. Such experiences may include headaches, tooth pain, joint or muscle pain. People are often exposed to situations that may cause pain such as illness, injury, dental procedures or surgery.

We are interested in the types of thoughts and feelings that you have when you are in pain. Listed below are thirteen statements describing different thoughts and feelings that may be associated with pain. Using the following scale, please indicate the degree to which you have these thoughts and feelings when you are experiencing pain.

0 – not at all; 1 – to a slight degree; 2 – to a moderate degree;
3 – to a great degree; 4 – all the time

When I'm in pain ...

- 1 I worry all the time about whether the pain will end.
- 2 I feel I can't go on.
- 3 It's terrible and I think it's never going to get any better.
- 4 It's awful and I feel that it overwhelms me.
- 5 I feel I can't stand it anymore.
- 6 I become afraid that the pain will get worse.
- 7 I keep thinking of other painful events.
- 8 I anxiously want the pain to go away.
- 9 I can't seem to keep it out of my mind.
- 10 I keep thinking about how much it hurts.
- 11 I keep thinking about how badly I want the pain to stop.
- 12 There's nothing I can do to reduce the intensity of the pain.
- 13 I wonder whether something serious may happen.

...Total

Updated 11/11

Most Effective Opioid Analgesia in Ambulatory Surgeries: a randomized control, investigator blinded, parallel group with superiority design study of Morphine versus Hydromorphone

[name], Principal Investigator SJHH

[name], Principal Investigator HHS

HADS: HOSPITAL ANXIETY DEPRESSION SCORE

This questionnaire is designed to help us know how you feel. Read each item and place a firm tick in the box opposite the reply, which comes closest to how you have been feeling in the past week.

Don't take too long over your replies; your immediate reaction to each item will probably be more accurate than a long thought-out response.

Tick one box only in each section

1 I feel tense or wound up:

Most of the time (3)
A lot of the time (2)
Time to time, occasionally (1)
Not at all (0)

8 I feel as if I am slowed down:

Nearly all the time (3)
Very often (2)
Sometimes (1)
Not at all (0)

2 I still enjoy the things I used to enjoy:

Definitely as much (0)
Not quite so much (1)
Only a little (2)
Hardly at all (3)

9 I get a sort of frightened feeling like "butterflies" in the stomach:

Not at all (0)
Occasionally (1)
Quite often (2)
Very often (3)

3 I get a sort of frightened feeling as if something awful is about to happen:

Very definitely and quite badly (3)
Yes, but not too badly (2)
A little, but it doesn't worry me (1)
Not at all (0)

10 I have lost interest in my appearance:

Definitely (3)
I don't take so much care as I should (2)
I may not take quite as much care (1)
I take just as much care as ever (0)

4 I can laugh and see the funny side of things:

As much as I always could (0)
Not quite so much now (1)
Definitely not so much now (2)
Not at all (3)

11 I feel restless as if I have to be on the move:

Very much indeed (3)
Quite a lot (2)
Not very much (1)
Not at all (0)

5 Worrying thoughts go through my mind:

A great deal of the time (3)
A lot of the time (2)
From time to time but not too often (1)
Only occasionally (0)

12 I look forward with enjoyment to things:

As much as I ever did (0)
Rather less than I used to (1)
Definitely less than I used to (2)
Hardly at all (3)

6 I feel cheerful:

Not at all (3)
Not often (2)
Sometimes (1)
Most of the time (0)

13 I get sudden feelings of panic:

Very often indeed (3)
Quite often (2)
Not very often (1)
Not at all (0)

7 I can sit at ease and feel relaxed:

Definitely (0)
Usually (1)
Not often (2)
Not at all (3)

14 I can enjoy a good book or radio or TV programme:

Often (0)
Sometimes (1)
Not often (2)
Very seldom (3)

ANXIETY SCORE _____ DEPRESSION SCORE _____

Most Effective Opioid Analgesia in Ambulatory Surgeries: a randomized control, investigator blinded, parallel group with superiority design study of Morphine versus Hydromorphone
[name], Principal Investigator SJHH
[name], Principal Investigator HHS

OUTCOMES AT 24 HOURS

24 hours after surgery (telephonic follow up)

- One-two calls shall be done during the next day; if unanswered, a repeat call will be made on the subsequent day (2nd day after discharge)
- For responders, the following questions will be asked.

1. What was your average pain score over the last 24 hrs, in 0-10 NAS scale, after you were discharged home?
2. After discharge, did you have nausea-severe enough to require medications at home?
3. After discharge, did you have vomiting-severe enough to require medications at home?
4. After discharged home, did you require a visit to ER, or readmission?

OUTCOMES AT 3 MONTHS AFTER SURGERY

1. **Persisting pain after Surgery:** Yes or No
2. **If Yes: Intensity of Pain:** a score between 0-10
3. **Brief Pain Inventory Items Score:**

Mark the box beside the number that describes how, during the past 24 hours, pain has interfered with your:			
1	General Activity	0-does not interfere 10-completely interferes	
2	Mood	0-does not interfere 10-completely interferes	
3	Walking Ability	0-does not interfere 10-completely interferes	
4	Normal Work (includes both work outside the home and housework)	0-does not interfere 10-completely interferes	
5	Relations with people	0-does not interfere 10-completely interferes	

Most Effective Opioid Analgesia in Ambulatory Surgeries: a randomized control, investigator blinded, parallel group with superiority design study of Morphine versus Hydromorphone
 [name], Principal Investigator SJHH
 [name], Principal Investigator HHS

6	Enjoyment of life	0-does not interfere 10-completely interferes	
7	Sleep	0-does not interfere 10-completely interferes	

4. Patient Global Impression of Change:

Since surgery, how would you describe the change (if any) in ACTIVITY LIMITATIONS, SYMPTOMS, EMOTIONS, and OVERALL QUALITY OF LIFE, related to your painful condition? Please circle the number below that matches your degree of change since beginning care at this clinic for the above stated chief complaint.

No change	Almost the same	A little better	Somewhat better	Moderately better	Better	A great deal better
1	2	3	4	5	6	7

5. Analgesic Use:

Did you have to use any pain medications for more than 1 month, to help with pain, which started with or after Surgery?

Yes:

No:

